5.2 Analysis Sets

Five analysis sets will be used: The Per-Protocol Analysis Set (PPAS), the Full Analysis Set (FAS), the Safety Analysis Set (SafAS), the Screened Subjects set, and the Randomized Subjects set.

5.2.1 Full Analysis Set

The FAS is defined as the subjects who received either CYD dengue vaccine or placebo and had blood sample drawn and valid post-injection serology results (ie, a result different from “not-reportable” [“NR”] or missing, for at least one dengue serotype).

Subjects will be analyzed by the vaccine treatment group to which they were randomized.

5.2.2 Per-Protocol Analysis Set

The PPAS is a subset of the FAS. The subjects presenting with at least one of the following relevant protocol deviations will be excluded from the PPAS:

- Subject did not meet all protocol-specified inclusion criteria or met at least one of the protocol-specified exclusion criteria
- Subject did not complete the vaccination schedule
- Subject received a vaccine other than the one that he / she was randomized to receive
- Preparation and / or administration of vaccine was not done as per-protocol
- Subject did not receive vaccine in the proper time window
- Subject did not provide post-dose serology sample in the proper time window or a post-dose serology sample was not drawn
- Subject received a protocol-prohibited medication (see protocol Section 6.7)
- Subject’s post-injection serology sample did not produce a valid test result (ie, a result different from “NR” or missing, for at least one dengue serotype)
- Subject had other protocol violations that affected the subject’s immune response, as determined by the clinical team before locking the database.

Subjects will remain in the corresponding population as long as they do not meet one of the above criteria.

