Although the ESDR performed when the 20 first subjects have received the first injection does not require the unblinding of data, unblinding can be performed at this review, if required. Moreover, some unblinded analyses may be provided by an independent Sanofi Pasteur statistician (ie, not involved either in the study or in the Dengue project) upon IDMC request.

A planned analysis will be performed on data collected up to 28 days post-Inj 3 of the last subject enrolled. This analysis will require the unblinding of data.

A second and final analysis will be performed at the end of the study.

Testing performed within GCI and GCI outsourced laboratories are blinded with respect to study treatment Group assignment. The code(s) linking information on sample vials to study treatment Group assignment are retained by the Clinical Department and cannot be accessed by GCI or contract laboratory testing personnel.

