12.2.3 Per-Protocol Analysis Set

The per-protocol analysis set (PPAS) is a subset of the FAS. The subjects presenting with at least one of the following relevant protocol deviations will be excluded from the PPAS:

- Subject did not meet all protocol-specified inclusion criteria or met at least one of the protocol-specified exclusion criteria
- Subject did not complete the vaccination schedule
- Subject received a vaccine other than the one that he / she was randomized to receive
- Preparation and / or administration of vaccine was not done as per-protocol
- Subject did not receive vaccine in the proper time window
- Subject did not provide post-dose serology sample in the proper time window or a post-dose serology sample was not drawn
- Subject received a protocol-prohibited medications (see [Section 6.7](#))
- Subject’s post-injection serology sample did not produce a valid test result (ie, a result different from “NR” or missing, for at least one dengue serotype)

A PP set will be defined for each vaccination. Subjects will remain in the corresponding population as long as they do not meet one of the above criteria.

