5.2.5 Populations Used in Analyses

The SafAS will be used for the description of clinical safety data. Subjects will be analyzed according to the product they actually received.

The immunogenicity analyses will be performed on the PPAS and will be confirmed on the FAS.

Screened subjects and randomized subjects will be used for various standard population tables including duration of the study, disposition of participants and deviations. Demographic and baseline characteristics will be presented on the PPAS, FAS and SafAS.

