5.6 Data Review for Statistical Purposes

A treatment blind review of the data has been anticipated through the data review process led by data management before database lock. This review of the data included a statistical review.

In the context of this study (ie, HIV-positive adults), a blinded early safety data review will be performed when the first 20 subjects have received the first injection and have provided safety data for Days 0-14 post-first injection on the following safety endpoints:

- Immediate (within 30 minutes) AEs
- Solicited injection site and systemic reactions
- Unsolicited AEs reported as related by the investigator within 14 days after the first injection
- SAEs and AESIs (including serious and non-serious AESIs)

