5.7 Changes in the Conduct of the Trial or Planned Analyses

Subjects had other protocol violations that affected the subject's immune response (as determined by the clinical team before locking the database) has been added as one of the criteria for the PPAS definition in [Section 5.2.2](#) taking the study population being HIV-positive adults treated with ARTs into account.

The age computed automatically in the eCRF, and presented as an integer.

The Sponsor decided to add a second test, with a higher sensitivity, ie, an ELISA (Anti-Dengue IgG ELISA commercialized by Euroimmun) to screen potential study participants. Both tests are very specific. The two tests will be performed sequentially. RDT will be performed first, and IgG ELISA will only be performed on subjects who tested negative for RDT. These changes are presented in details in [Section 3](#).

Some endpoints derivation were updated in Section [4.4.1.2.2](#), [4.4.1.5.6](#) and [5.3.1.5](#) per latest Safety Task Force Guideline 8.0.

No interim analysis on data obtained up to Day 28 after the last injection of the last subject will be performed. The full trial results will be released in once in the final CSR.

6 References List

- 1 Gubler DJ. Dengue. In: Epidemiology of arthropod-borne viral disease. Monath TPM, editor, Boca Raton (FL): CRC Press, 1988:223-60
- 2 World Health Organization. Dengue and dengue haemorrhagic fever, Fact sheet N°117, Updated May 2015. [Accessed on 24 November 2015]. Available from URL: <http://www.who.int/mediacentre/factsheets/fs117/en/>
- 3 World Health Organization. Guidelines on the quality, safety and efficacy of dengue tetravalent vaccines (live, attenuated). WHO Expert Committee on Biological Standardization. WHO Technical Report Series No. 979, 2013. Annex 2
- 4 World Health Organization. Dengue: Guidelines for diagnosis, treatment, prevention and control. Geneva: WHO Press. 2009. WHO/HTM/NTD/DEN/2009.1

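### The per-protocol exclusion added in the SAP refers to the immune response itself, and nothing keeps post-injection titers from the team that applies it

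*SAP*

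**What the plan says.** Protocol 12.2.3 lists eight deviations that remove a subject from the per-protocol analysis set (PPAS). The last concerns assay validity: "Subject’s post-injection serology sample did not produce a valid test result". None of the eight depends on what happened to the immune response.

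SAP 5.2.2 repeats these eight and adds a ninth: "Subject had other protocol violations that affected the subject’s immune response, as determined by the clinical team before locking the database". SAP 5.7 declares that this "has been added as one of the criteria for the PPAS definition", and the reason given is "taking the study population being HIV-positive adults treated with ARTs into account". Neither section lists the violations in view or says how an effect on the response is to be established.

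SAP 5.2.5 makes the PPAS the main set: "The immunogenicity analyses will be performed on the PPAS and will be confirmed on the FAS". On blinding, SAP 5.6 states: "A treatment blind review of the data has been anticipated through the data review process led by data management before database lock". Protocol 11.3 also provides for a blind review before lock, and Protocol 6.4 keeps the testing laboratories blind to group.

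**The concern.** An exclusion from an analysis set should rest on what was done to the subject, not on the result being estimated. Here the violation must have *affected* the response, where *may affect* would have been enough. A reviewer with the titers at hand could read this as an invitation to consult them: of two subjects with the same irregularity, the one with the poor titer might be excluded and the other kept.

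The natural direction of such a bias is favorable to the vaccine. Protocol 1.4 and 5.1.2 ask whether HIV-positive adults respond less well than immunocompetent people. Selective loss of low responders would raise the geometric mean titers (GMTs), the titer ratios and the percentages above a threshold, which are the immunogenicity summaries in SAP 5.1.2.2. No hypothesis is tested, so the stake is bias in the descriptive estimates and not type I error.

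**Working it through.** **1. Is there room for titers to enter the decision?**

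- *Timing.* The decision comes before database lock. SAP 5.4 and 5.7 cancel the analysis at Day 28 after the last injection, so the only analysis follows the final lock. The last PRNT sample is taken at Visit 8, 28 days after injection 3, and the 6-month safety follow-up comes later. Every titer time point therefore precedes the lock.
- *Data flow.* Protocol 11.2 has laboratory results checked and integrated before the database is released for analysis.
- *Blinding.* SAP 5.6 and Protocol 11.3 blind the review to treatment. Protocol 6.4 blinds laboratory staff to group. Neither withholds post-injection PRNT results from the clinical team.
- *Scope.* The other eight criteria already cover eligibility, incomplete schedule, wrong product, preparation or administration, vaccination window, sampling window or missing sample, Section 6.7 medications and invalid results. The ninth criterion reaches only violations outside that list.

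The documents do not say that titers will be consulted. They leave it possible.

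**2. How large could the effect be?**

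The plan has no figure to reproduce on this point. Its only design figure, in SAP 5.5, does reproduce (1 − 0.97^100 = 95.2%, against 95% stated), but this point does not depend on it.

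Inputs: n = 100 vaccinees (SAP 5.5). Assumed, because the documents are silent: log10 titers normal with SD *s* = 0.4, 0.6 or 0.8, and *k* = 3, 5 or 10 exclusions, all in the vaccine group.

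If the removed subjects have mean *m* in SD units, with the full group at 0, the mean log10 titer rises by −*k*·*m*/(*n* − *k*) SDs, and the GMT is multiplied by 10 to the power (shift × *s*). The values of *m* come from 40,000 simulated samples of 100 normal values.

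- *Five removed at random from the lower half:* m = −0.790, shift = 5 × 0.790/95 = 0.0416 SD. GMT factor 10^(0.0416 × 0.4) = 1.039, and 1.059 and 1.080 for s = 0.6 and 0.8.
- *The five lowest removed (upper bound for k = 5):* m = −2.019, shift = 5 × 2.019/95 = 0.1063 SD. GMT factor 10^(0.1063 × 0.4) = 1.103, and 1.158 and 1.216 for s = 0.6 and 0.8.

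| k | random from lower half, s = 0.4 to 0.8 | k lowest, s = 0.4 to 0.8 |
|---|---|---|
| 3 | 1.023 to 1.046 | 1.065 to 1.134 |
| 5 | 1.039 to 1.080 | 1.103 to 1.216 |
| 10 | 1.084 to 1.176 | 1.194 to 1.425 |

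For a percentage above a threshold, again at the extreme: if the true result is 80/100 = 80% and all five removed are non-responders, it becomes 80/95 = 84.2%. The 80% is also an assumption.

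**The case against.** There is a good deal to say for the plan. A violation is required first, and it must fall outside eight fairly complete criteria, so few subjects should qualify. Whether a violation compromised the response can be judged from its type and timing without seeing a titer. The decision precedes lock, the review is treatment-blind, and the change is declared. The analysis is repeated on the full analysis set (FAS), where the exclusion does not apply. The direction is not certain either: a violation that boosts antibody would remove high titers and lower the GMT.

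Most of this stands and limits the size of the problem. It does not close the gap. The wording permits a judgment from type and timing but does not require it. The FAS also retains subjects with the other deviations, so a PPAS–FAS difference could not be traced to this criterion.

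Three stronger readings are tempting, and the documents do not support them:

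- *Subjects can be dropped for a low titer.* They cannot; a protocol violation is needed.
- *Titers and viremia disclose the arm, so the treatment blind is empty.* Protocol 1.2 reports vaccinal viremia in only 4.5% of adults, so on that figure it would be absent in about 95% of vaccinees. All subjects are screened as dengue-seropositive and so are expected to have antibody at entry, and no titer distribution is given that would show PRNT results to identify the group.
- *The deciding team holds the treatment codes.* Protocol 6.4 says "The code(s) linking information on sample vials to study treatment Group assignment are retained by the Clinical Department", in a paragraph about keeping laboratory staff blind. Nothing links that department to the team that decides PPAS membership. Custody of these codes is a separate question.

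**Conclusion.** The point holds in a limited form. The ninth criterion is open-ended, is worded in terms of the outcome, and is applied when all titers may be visible. Titers can therefore influence which subjects with an unlisted violation leave the main immunogenicity set.

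The likely effect is modest. For five exclusions among 100 vaccinees it is about 4 to 8% on the GMT if removals come at random from the lower half of titers. The 10 to 22% from removing the five lowest is an upper bound for that number, not a prediction. Both rest on the assumed number of exclusions, the assumed SD of 0.4 to 0.8 and normal log10 titers. The effect is zero if no one is excluded under this criterion or if exclusion is unrelated to titer.

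The study is descriptive and immunogenicity is secondary, so this does not threaten the primary safety objective. It is worth correcting because the remedy is cheap.

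**What to change.** In SAP 5.2.2, replace the ninth bullet with violations that *may affect* the immune response, judged by type and timing from a list fixed in the SAP. The list should cover cases beyond the existing bullets. Other vaccines, blood products and immunosuppressants are already Category 2 in Protocol 6.7, which an existing bullet cites, so repeating them adds nothing. If the HIV and antiretroviral background prompted the addition, the specific events in mind should be named.

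In SAP 5.6, require per-subject decisions to be signed before post-injection PRNT and vaccinal viremia results are released to the deciding team. Baseline PRNT must stay available, because Protocol 5.1.1 uses it before injection 2. CD4 count and HIV RNA should not be withheld either: they feed the vaccination contraindications (Protocol 5.2.7), the study holds (5.5) and SAE reporting (10.7).

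Report the number excluded under this criterion by group.

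The cost is SAP wording and an access restriction during data review. Unforeseen violation types stay in the PPAS and are handled by a sensitivity analysis that leaves those subjects out.

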5.2.7.2 Definitive Contraindications

Should a subject experience 1 of the conditions listed below, the Investigator will discontinue vaccination:

- 1) Pregnancy, as indicated by a positive urine test
- 2) Dengvaxia® administered inadvertently during the study (eg, as part of a vaccination campaign)
- 3) An anaphylactic or other significant allergic reaction to the previous dose of vaccine
- 4) Abnormal laboratory parameter of Grade 2 or 3 and assessed by the Investigator as related to the previous dose of vaccine
- 5) Subject deprived of freedom by an administrative or court order, or in an emergency setting, or hospitalized without her/his consent
- 6) Self-reported or suspected congenital or acquired immunodeficiency, except HIV, or receipt of immunosuppressive therapy such as anti-cancer chemotherapy or radiation therapy within the preceding 6 months, or long-term systemic corticosteroids therapy (prednisone or equivalent for more than 2 consecutive weeks within the past 3 months)
- 7) Ongoing clinical AE related to the previous study vaccination, and in the Investigator's opinion, contraindicating further vaccination
- 8) SAE related to the study vaccine following the previous study vaccination
- 9) Confirmed CD4 count < 200 cells/mm³

Subjects will not be withdrawn due to contraindication but will be followed-up for safety. Subjects will not be replaced.

If a female subject who has already received at least one injection becomes pregnant during the study, she will continue to be followed for safety assessments until delivery or until 6 months after the last injection, whichever is the latest. No additional injections will be administered.

Subjects with a definitive contraindication will continue to be followed-up for the study-defined safety and immunogenicity assessments, as applicable.

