12.1 Statistical Methods

All statistical analyses will be performed under the responsibility of the Sponsor's Biostatistics Platform using the SAS® software, at least version 9.3 (SAS Institute, Cary, NC, USA).

A statistical analysis plan (SAP) will be written and peer reviewed before any analyses. In accordance with the protocol, the SAP will describe all analyses to be performed under the responsibility of the Sponsor and all the conventions to be taken.

A statistical analysis of the safety and immunogenicity data obtained up to Day 28 after the last injection of the last subject enrolled will be conducted once data are available and an interim database lock has been conducted. A final analysis will be conducted once the 6-month safety data have been collected and the final database lock has occurred. No multiplicity adjustment is necessary because no hypotheses will be tested.

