12.1.2.2 Statistical Methods

The proportion of subjects with a detected and quantified CYD dengue vaccinal viremia (ie, above the detection level) whatever the serotype (as assessed by YF RT-PCR) and for each of the 4 dengue serotypes (by serotype-specific RT-PCR method) after the first CYD dengue vaccine injection will be presented.

A summary of CD4 count and HIV-1 RNA viral load over time will be presented.

Analysis of dengue neutralizing antibody levels will be performed in each vaccine Group before first injection (at baseline) and 28 days after each injection using:

- GMTs against each serotype with the parental dengue virus strains
- GM of individual titer ratio (GMTR) against each serotype with the parental dengue virus strains (post-Injection 2/pre-Injection 1, and post-Injection 3/pre-Injection 1)

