5.1.2.2 Statistical Methods

For descriptive purposes, the statistics presented on Table 5.1 will be produced.

The proportion of subjects with a detected and quantified CYD dengue vaccinal viremia (ie, above the detection level) whatever the serotype (as assessed by YF RT-PCR) and for each of the four dengue serotypes (by serotype-specific CYD RT-PCR method) after the first CYD dengue vaccine injection will be presented at V02 and V03.

Number of subjects and percentages having a decrease in CD4 > 30% post-injection compared to pre-injection values and confirmed decrease in CD4 > 30% after each injection, not explained by non-adherence to ART and not explained by any other possible etiology, as well as an increase in HIV viral load post-injection and confirmed increase in HIV viral load (ie, plasma HIV-1 RNA < 50 copies/mL pre-injection and > 1000 copies/mL post-injection) for each injection, not explained by non-adherence to ART and not explained by any other possible etiology will be presented.

Analysis of dengue neutralizing antibody levels will be performed in each vaccine group before first injection (at baseline) and 28 days after each injection using:

- GMTs against each serotype with the parental dengue virus strains
- GM of individual titer ratio (GMTR) against each serotype with the parental dengue virus strains (post-Injection 1/pre-Injection 1, post-Injection 2/pre-Injection 1, and post-Injection 3/pre-Injection 1)
- Number and percentage of subjects ≥ 10 (1/dil) against each dengue serotype with the parental dengue virus strains at each available time point
- Number and percentage of subjects ≥ 10 (1/dil) against at least 1, 2, 3, or 4 dengue serotypes with the parental dengue virus strains at each available time point
- Number and percentage of subjects \geq various titer thresholds (1/dil) against each dengue serotype with parental dengue virus strains at each available time point
- Number and percentage of subjects \geq various titer thresholds (1/dil) for at least 1, 2, 3, or 4 serotypes with parental dengue virus strains at each available time point
- Distribution of titers against each of the 4 serotypes with parental dengue virus strains at each available time point and corresponding RCDCs
- Number and percentage of subjects immune and non-immune to YF, dengue, Zika and FV statuses at baseline

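### SAP 5.2.2 drops, without declaring it in 5.7, the protocol rule of one per-protocol set per vaccination; read literally, later-dose deviations would remove valid earlier titers from the main immunogenicity analysis.

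*SAP*

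**What the plan says.** Protocol 12.2.3 defines the PPAS as a subset of the FAS and lists the deviations that exclude a subject. Among them are an incomplete vaccination schedule, an injection outside its window, and a post-dose sample that is missing or outside its window. Two sentences close the section. The first is "A PP set will be defined for each vaccination". The second keeps a subject in the matching population until an exclusion is met.

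SAP 5.2.2 carries the same list, including "Subject did not complete the vaccination schedule", and adds one criterion for other violations affecting the immune response. It then goes straight to "Subjects will remain in the corresponding population as long as they do not meet one of the above criteria". The sentence on one set per vaccination is absent, and no other part of the SAP supplies it. SAP 5.2 counts five analysis sets, one of which is the PPAS. SAP 5.2.5 runs immunogenicity on the PPAS and confirms it on the FAS.

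SAP 5.7 lists changes to the planned analyses. On the PPAS it says only that the new criterion "has been added as one of the criteria for the PPAS definition".

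**The concern.** The PPAS is the main population for the immunogenicity objective, and titers are summarised at baseline and 28 days after each of three injections. With one set per vaccination, a subject who is compliant through injection 1 contributes to the post-injection-1 results whatever happens later. With a single set and criteria that carry no dose index, the same subject drops out of every time point after a missed or late injection 3. Post-injection-1 and post-injection-2 summaries would then describe only subjects who went on to complete everything correctly. That is selection on future events, and the protocol's rule avoids it. Two programmers working from the SAP could also build different sets, each with a defensible reading.

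**Working it through.** **Text comparison**

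| Element | Protocol | SAP |
|---|---|---|
| Exclusion list | 12.2.3, no dose index | 5.2.2, same list plus one item, no dose index |
| One set per vaccination | Stated in 12.2.3 | Absent |
| Subjects remain in the corresponding population | Follows the rule above | Retained without the rule |
| Number of PP sets | One per vaccination, so three | 5.2 names one PPAS |
| Removal declared | n/a | Not in 5.7 |

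**What the literal reading does**

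- Deviation at injection 2 or its sample: baseline and post-injection-1 titers leave the PPAS, though both were valid.
- Deviation at injection 3 or its sample: baseline, post-injection-1 and post-injection-2 titers leave the PPAS.

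**Size**

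The plan gives no PPAS deviation rate and no projected PPAS size, so there is no figure of its own to reproduce on this point. The illustration takes the planned group sizes (N = 100 CYD, N = 50 placebo; SAP 5.5) and assumes that k subjects deviate only at a later dose or sample, with no other exclusions. SAP section 5 specifies a Student t interval on log10 titers. For the same standard deviation, which cancels, the ratio of half-widths is

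[t(0.975, n−1)/√n] ÷ [t(0.975, N−1)/√N], with n = N − k.

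| Group | k | n | t(n−1)/√n | t(N−1)/√N | Ratio | Widening |
|---|---|---|---|---|---|---|
| CYD | 5 | 95 | 0.2037 | 0.1984 | 1.027 | 2.7% |
| CYD | 10 | 90 | 0.2094 | 0.1984 | 1.056 | 5.6% |
| CYD | 20 | 80 | 0.2225 | 0.1984 | 1.122 | 12.2% |
| Placebo | 5 | 45 | 0.3004 | 0.2842 | 1.057 | 5.7% |
| Placebo | 10 | 40 | 0.3198 | 0.2842 | 1.125 | 12.5% |

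For a possible shift, assume that the k excluded subjects have titers two-fold lower (or higher) than the rest. Dropping them moves the GMT up (or down) by the factor 10^((k/N) × log10 2) = 2^(k/N). For CYD with k = 5, 10 and 20 this is 2^0.05 = 1.04, 2^0.10 = 1.07 and 2^0.20 = 1.15. Both k and the two-fold difference are assumptions; neither comes from the documents.

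**The case against.** The strongest reply is that nobody intended a change. Protocol 12.1 states "In accordance with the protocol, the SAP will describe all analyses to be performed", so an analyst holding both documents already has the rule. The retained sentence about remaining in a population fits a dose-by-dose scheme better than a single set. The SAP also takes more interest in early time points than the protocol does: protocol 12.1.2.2 lists the ratios "post-Injection 2/pre-Injection 1, and post-Injection 3/pre-Injection 1", while SAP 5.1.2.2 lists "post-Injection 1/pre-Injection 1, post-Injection 2/pre-Injection 1, and post-Injection 3/pre-Injection 1". All of this favours a drafting slip, and that part of the reply stands. It does not remove the problem. The SAP is the document that is programmed from, it names one PPAS, and its list of changes covers the PPAS definition without mentioning this rule.

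Three further objections also stand and limit the point. The retained phrase can be read as meaning the single PPAS, so it is not strictly without a referent. The criteria lack a dose index in the protocol too, so adding one goes a step beyond restoring the protocol text. And the consequences are contained: no hypotheses are tested, the FAS has no schedule or window exclusions and keeps these titers, and safety uses its own analysis set.

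A reader might infer more than the documents support.

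- **The sponsor deliberately moved to a single three-dose PPAS.** No SAP sentence says that one set applies to all time points.
- **The early results will be biased in a known direction.** Neither the size nor the sign of any effect can be derived.
- **Screen-positive, PRNT-negative subjects, whose injections stop by design, would be wrongly lost.** The documents treat them as not previously exposed, and the objective concerns exposed adults, so leaving them out of a per-protocol summary is not clearly a loss.
- **Immunogenicity follow-up continues after a definitive contraindication (protocol 5.2.7.2), so data are being discarded.** This adds little, because titers taken before a stop exist whether or not follow-up continues.

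**Conclusion.** The point holds as an undeclared inconsistency between protocol 12.2.3 and SAP 5.2.2 that is worth correcting. The harm is conditional on the SAP being applied literally. In that case, deviations at later doses or samples remove valid earlier titers from the main immunogenicity set, and the early GMT, GMTR and threshold results are selected on later events. Under the assumed losses the effect is modest: 2.7% to 12.2% wider log10 intervals for CYD with 5 to 20 subjects lost, and 5.7% to 12.5% for placebo with 5 to 10 lost. A GMT shift of at most a factor of 1.15 follows if 20 CYD subjects are lost and they differ two-fold from the others. The reach is confined to secondary, descriptive analyses that are repeated on the FAS. The primary safety objective is not affected.

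**What to change.** Before unblinding, put the protocol's sentence on one PP set per vaccination back into SAP 5.2.2 and make SAP 5.2 consistent with it. State that the schedule, window and sample criteria apply only up to injection k and its post-dose sample, and that this set is used for post-injection-k results. If a single three-dose PPAS is what the sponsor wants, declare and justify it in SAP 5.7 and reword the retained sentence.

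The cost is one restored sentence, a dose index on the criteria and three population flags. The downside is that the analysed n differs by time point, as the protocol already planned.
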